9.0 Confidentiality, Privacy and Data Management

See the Research Data Plan Review Form

10.0 Data and Safety Monitoring Plan

10.1 Periodic evaluation of data

Adverse event reporting will be reviewed at regular research meetings led by [name]. Annual reports will be made to the Penn State IRB as per the current protocol.

10.2 Data that are reviewed

The primary safety parameters we will collect are patient discomfort as determined by VAS scores, any serious sequelae to Sono HSG including allergic reactions, infection, development of adhesions, subsequent related surgeries or hospitalizations.

10.3 Method of collection of safety information

The occurrence of an AE or SAE may come to the attention of study personnel during study visits and interviews of a study participant presenting for medical care, or upon review by a study monitor, [name]. All AEs will be captured on the appropriate CRF and include event description, time of onset, clinician's assessment of severity, relationship to study product (assessed only by those with the training and authority to make a diagnosis), and time of resolution/stabilization of the event.

10.4 Frequency of data collection

The PI will record all reportable events with start dates occurring any time after informed consent is obtained until 7 (for non-serious AEs) or 30 days (for SAEs) after the last day of study participation. At each study visit, the investigator will inquire about the occurrence of AE/SAEs since the last visit. Events will be followed for outcome information until resolution or stabilization.

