7.2 Study Procedures

	Screening	Enrollment/Study Visit Time = 0	Post Procedure = 2 – 4 weeks	Final Study Contact Time = 6 mos (+2 weeks)	Pregnancy Follow up Up to 15 mos
Inclusion/Exclusion Criteria	X				
Review Informed Consent and Obtain Per Telephone	X				
Schedule Sono HSG	X				
Collect Written Informed Consent		X			
Randomize		X			
Perform Urine Pregnancy Test		X			
Perform Sono HSG with Saline and then Study Agent		X			
Administer FertiQol Questionnaire		X		X	
Assess Patient VAS score		X			
Assess echogenicity of study media		X			
Assess adequacy of blinding by patient and physician		X			
Obtain Blood for Anti-Chlamydial Antibodies		X			

	Screening	Enrollment/Study Visit Time = 0	Post Procedure = 2 – 4 weeks	Final Study Contact Time = 6 mos (+2 weeks)	Pregnancy Follow up Up to 15 mos
Obtain blood for TSH and Free T4		X	X		
Collect adverse events since test				X	
Obtain Release of Pregnancy Records as necessary					X
Collect all pregnancy outcomes					X

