7.2.5 Follow Up (up to 15 months)

Follow up will take place via review of medical records. Patients will follow American Society of Reproductive Medicine (ASRM) guidelines for treatment.(13) Currently, based on Level I evidence that would be clomiphene/IUI for unexplained infertility (14) and letrozole with timed intercourse for polycystic ovary syndrome.(15) The initial consent will allow access to all medical records in the Electronic Health Record including any resulting pregnancy. Data collected will include any potential adverse events as well as information on the participant's course of infertility treatment/any resulting pregnancy outcomes up to 15 months after the procedure. If a patient seeks infertility or pregnancy care outside the institution we will obtain a release of records form from the patient at their last visit to our infertility clinic to obtain release of these records at the end of the 6 month participation in the study (or longer if a patient conceives at the end of the 6 month window of study participation). We will not follow any conceptions that occur more than 6 months after performing the Sono SHG. A conception is defined as a positive urine or serum pregnancy test for hCG. All conceptions will be followed up to the completion of that pregnancy.

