7.3 Duration of Participation

Study duration will typically be 6 months(+2weeks), but can be up to 15 months if conception occurs at the end of study period.

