10.7 Statistical tests

A Pearson's chi-square test, or Fisher's exact test if the expected cell counts are <5, will be used to compare each reported AE between the Lipiodol UF® and saline groups, provided there are sufficient AEs to obtain inference.

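### The plan gives conflicting adverse-event windows, and the one formed by 10.4 and 7.3 makes the length of safety observation depend on whether a woman conceives

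*Combined protocol and SAP*

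**What the plan says.** All references are to the combined protocol and SAP.

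- **10.4** records events from consent "until 7 (for non-serious AEs) or 30 days (for SAEs) after the last day of study participation".
- **7.3** makes that last day depend on outcome: "Study duration will typically be 6 months(+2weeks), but can be up to 15 months if conception occurs at the end of study period".
- **7.2.5** adds "All conceptions will be followed up to the completion of that pregnancy", but also "We will not follow any conceptions that occur more than 6 months after performing the Sono SHG". On adverse events it says: "Data collected will include any potential adverse events as well as information on the participant's course of infertility treatment/any resulting pregnancy outcomes up to 15" (the figure counts months from the Sono HSG). It does not say whether this covers every woman or only those who conceive.
- **7.2 (schedule)** has one AE row, "Collect adverse events since test". Its single mark appears to sit under the 6-month (+2 weeks) final contact. The pregnancy follow-up column carries only the records release and pregnancy outcomes.
- **10.3** captures all AEs, with description, onset, severity and relationship to product.
- **10.7** states that a chi-square or Fisher test "will be used to compare each reported AE between the Lipiodol UF® and saline groups", if there are enough events. It sets no common cut-off, exposure adjustment, restriction to related events or separate handling of obstetric events.

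**The concern.** Safety and tolerability is the co-primary objective (1.1), and the hypothesis in 2.3 is more ongoing pregnancies with safety equal to saline. Taken together, 10.4 and 7.3 tie the length of safety observation to conception, which happens after randomisation and leads directly to the efficacy endpoint. If the efficacy hypothesis is true, more women in the Lipiodol arm stay under observation longer. The extra time falls entirely in pregnancy, when obstetric complications and delivery admissions occur. An agent with no toxicity would then tend to show more AEs than saline. The pilot is meant to supply estimates for a larger trial, so a distorted AE rate could be carried forward even without a significant test.

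**Working it through.** **Inputs.** Ongoing pregnancy 39.2% v 28.5% from the prior trial (2.2), used only as illustration. Window without conception 6.5 months and maximum with conception 15 months (7.3). 25 evaluable women per arm (8.2). Assumed: an average window for women who conceive of 10.5 or 12 months, with 15 as the ceiling, and an obstetric-AE rate of 10% to 70% per pregnancy, the same in both arms.

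**Reproducing the cited figure.** 0.392 / 0.285 = 1.375, stated as 1.38. With about 560 per arm (equal split of 1119 assumed), the standard error of the log relative risk is √(1/219.5 − 1/560 + 1/159.3 − 1/559) = 0.085. The 95% interval is 1.16 to 1.63, as stated.

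**Length of window.** For an individual, 15 / 6.5 = 2.3 at most. The arm mean is (1 − p) × 6.5 + p × c, where c is the window for women who conceive, so the arms differ by (0.392 − 0.285) × (c − 6.5). The added 7 or 30 days applies to both arms and cancels.

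| c (months) | Lipiodol | Saline | Difference |
|---|---|---|---|
| 10.5 | 8.07 | 7.64 | 0.43 |
| 12 | 8.66 | 8.07 | 0.59 |
| 15 | 9.83 | 8.92 | 0.91 |

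Expected pregnancies are 25 × 0.392 = 9.8 and 25 × 0.285 = 7.1. Person-months beyond 6.5, all in women who conceive, are 9.8 × 5.5 = 54 v 7.125 × 5.5 = 39 at c = 12, and 83 v 61 at c = 15.

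**Obstetric AEs with a harmless agent.** The arm risk is p × q, where q is the rate per pregnancy. The relative risk is 0.392q / 0.285q = 1.38 for any q.

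| q | Lipiodol | Saline | Difference (points) | Chance of p<0.05, 25 per arm |
|---|---|---|---|---|
| 10% | 3.92% | 2.85% | 1.07 | 4% |
| 30% | 11.76% | 8.55% | 3.21 | 6% |
| 50% | 19.60% | 14.25% | 5.35 | 7% |
| 70% | 27.44% | 19.95% | 7.49 | 9% |

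The last column uses a normal approximation. At q = 30% the expected counts are 25 × 0.1176 = 2.9 v 25 × 0.0855 = 2.1 women, a difference of less than one.

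**Under each reading of the plan**

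- *10.4 with 7.3:* the windows differ as above, and late pregnancy and delivery fall inside them.
- *Schedule in 7.2:* everyone has 6.5 months, so the difference in length is 0. Pregnancy events inside that window still follow the pregnancy rate.
- *7.2.5 read as 15 months for all:* the lengths are equal. Obstetric events still arise only in pregnant women, and conceptions after 6 months are not followed.

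A common window therefore removes the difference in length, but not the obstetric contrast. That needs separate reporting.

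**The case against.** The strongest reply is that the schedule already does most of what is needed: one AE collection point at 6 months for everyone, with pregnancy outcomes on a separate row. Section 10.2 also centres the primary safety parameters on pain and on serious consequences of the procedure, including related surgery or hospitalisation. An ordinary delivery admission is not one of these. Section 10.7 tests events one by one, and only where numbers allow, so an obstetric complication would appear under its own name rather than inside a total. The term for reportable events in 10.4 is not defined. The cited rates come from a fluoroscopic trial against a water-based agent, whereas here both arms first receive saline.

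Much of this stands. A reader might infer that the plan has settled on unequal windows and that its co-primary safety result will count efficacy as harm. The documents do not support that. Only 10.4 with 7.3 gives unequal windows, and the schedule and one reading of 7.2.5 do not. Pain scores and immediate reactions are untouched. The pooled obstetric figures above illustrate scale and are not a test the plan specifies.

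What remains is that 10.4 is the section that sets the recording rule, and it conflicts with the schedule. Section 10.3 captures all AEs, and 10.7 limits its comparison neither to the 10.2 list nor to related events. Recording relationship to product does not help if the comparison does not use it.

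**Conclusion.** The concern holds as an unresolved inconsistency with a possible bias, not as an established difference in follow-up between arms. If 10.4 and 7.3 govern, and if Lipiodol raises pregnancy about as much as in the prior trial, the mean window is longer by about 0.4 to 0.9 months in the Lipiodol arm. Obstetric AEs would then be expected at a relative risk of about 1.38 with no toxicity.

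These figures assume the cited ongoing-pregnancy rates and equal obstetric risk per pregnancy. Conception rates would be higher than ongoing-pregnancy rates, while early losses would shorten some windows. Fifteen months is a maximum.

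A reader might also infer that the pilot is likely to report a significant excess of AEs. At 25 per arm the chance is only about 4% to 9%. The consequence lies in the descriptive AE rates, and in how equal safety is read when the larger trial is designed.

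**What to change.** - Reconcile the schedule in 7.2 with 7.2.5, 7.3 and 10.4, so that one AE recording window is stated and it is clear whom the record review to 15 months covers.
- State in 10.7 that the between-arm AE and SAE comparison uses one fixed window for every woman, from the procedure to the 6-month (+2 weeks) time point, with non-obstetric events as the main comparison.
- Tabulate obstetric, fetal and delivery events separately by randomised arm through completion of pregnancy. Any rate per pregnancy should be descriptive only, because it conditions on a post-randomisation outcome.
- List later procedure-related events, such as granuloma, adhesions and late effects of intravasation (long-term risks named in 11.0), descriptively for all women.

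The cost is mainly wording. Section 10.3 already records description and onset, so events can be classified and cut at the time point without new visits. If the review to 15 months was meant only for women who conceive, listing later events for everyone adds some chart review. The downside is that events after 6 months leave the main comparison and appear only in descriptive tables.

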7.2.3 Baseline Assessments/Study Intervention

Case report forms documenting the history will be obtained, the Ferti-QOL (12) quality of life survey will be obtained. Serum for Anti-Chlamydial antibodies as well as Free T4 and TSH will be drawn before or after the Sono HSG depending on the patient's reason for visit, as often a baseline progesterone and hCG level are obtained prior to the Sono HSG if the patient is to go on immediately to treatment. The rationale for the Anti-Chlamydial antibodies is that we have shown they are associated with failure to conceive and pregnancy loss including ectopic pregnancies in our prospective randomized controlled trials (9). Samples drawn for anti-chlamydial antibodies will be sent to the study sponsor's laboratory for analysis. Free T4 and TSH will be collected in order to assess thyroid function. A urine pregnancy test will be performed. We will then proceed with the Sono HSG. This begins first with a routine pelvic ultrasound. Then a speculum is inserted into the vagina and then the Sono HSG catheter is inserted through the cervical canal into the uterine cavity and the balloon is inflated to maintain a seal at the cervical canal. A special device, i.e. the FemVue system, will then be used to infuse normal saline while at the same time creating bubbles to ease ultrasound visualization. The speculum is removed and the transvaginal ultrasound probe is inserted. The Sono HSG begins with infusion of normal saline via the FemVue catheter. After a patient has had an SHG with a normal cavity and at least one patent tube as determined by the performing physician, the patient will receive the study contrast or control saline which will be in an opaque glass syringe and connected to the uterine catheter via opaque tubing to allow double blinding of physician and patient. The study agent will be shaken vigorously to induce turbulence and air bubbles to ease tracking of the agent and then infused in 2 cc increments under ultrasound

visualization while the physician again visualizes the uterine cavity and patency of the fallopian tube(s). Infusion will cease with documentation of a normal cavity and tubal patency or when 10 cc have been infused. The amount of contrast infused will be recorded. After infusion the patient will be asked to assess the degree of pain she experienced by the VAS scale and both physician and patient will be asked to document a guess as to what contrast medium was used as study agent.

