7.2.4 Post-Procedure Visit (2-4 weeks)

Participants will have a blood draw completed 2-4 weeks after the Sono HSG procedure to re-test TSH and Free T4.

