7.2.6 Final Study Contact (6 months + 2 weeks)

The final study contact will take place by mail. If the patient has not become pregnant, the patient will be mailed the follow up Ferti-QOL questionnaire to fill out with a self addressed prepaid return envelope. Any pregnancies that occur up to 6 months after randomization will be followed to completion and will not receive a FertiQol questionnaire.

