14.0 Subject Stipend (Compensation) and/or Travel Reimbursements

Participants who complete the FertiQol at final study contact, will receive a \$10 gift card. .

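### Section 10.4 requires an adverse event inquiry at each study visit, but the 7.2 schedule marks one only at the mailed 6-month contact; the clear gap is the 2-4 week visit.

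*Combined protocol and SAP*

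**What the plan says.** Section 10.4 sets the duty: "At each study visit, the investigator will inquire about the occurrence of AE/SAEs since the last visit". It also has events recorded from informed consent onward.

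The schedule in 7.2 has one AE row, "Collect adverse events since test", with one mark, in the 6-month column.

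The procedural sections read as follows.
- **7.2.3 (Time 0):** "After infusion the patient will be asked to assess the degree of pain she experienced by the VAS scale". The patient and physician also guess the contrast agent. No other AE inquiry is described.
- **7.2.4 (2-4 weeks):** "Participants will have a blood draw completed 2-4 weeks after the Sono HSG procedure to re-test TSH and Free T4". That sentence is the whole section.
- **7.2.5 (follow-up):** the method is medical record review, up to 15 months. "Data collected will include any potential adverse events".
- **7.2.6 (6 months):** the contact is by mail. "If the patient has not become pregnant, the patient will be mailed the follow up Ferti-QOL questionnaire". Women who conceive are not sent that questionnaire, and no AE question is described for either group.

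Section 6.2.2 repeats that records will be reviewed for AEs. Section 10.3 adds that "The occurrence of an AE or SAE may come to the attention of study personnel during study visits", when a participant is interviewed on presenting for care, or through monitor review.

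**The concern.** Two parts of one protocol give staff different instructions. Someone following 10.4 would ask about AEs at the 2-4 week visit. Someone following the schedule and 7.2.4 would take blood and not ask.

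The look-back differs as well. Section 10.4 asks about the interval since the previous visit, while the schedule row reaches back to the test.

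Safety and tolerability of the oil contrast is the co-primary objective (1.1), and 10.7 plans to compare each reported AE between arms where numbers allow. The pilot is also meant to inform a larger trial. Section 10.3 requires onset, severity, relationship to the study product and time of resolution for every AE. Those details are harder to recover at six months for bleeding, or for mild infective or allergic symptoms, in the days after infusion.

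**Working it through.** No formula applies, and the plan states no figure to reproduce. The check sets the schedule beside the text, contact by contact.

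| Contact | Mode | Does 10.4 call for an inquiry? | AE mark in 7.2? | AE content in the procedural text |
|---|---|---|---|---|
| Time 0 | In person | Yes | No | Pain score only (7.2.3) |
| 2-4 weeks | In person | Yes | No | None; TSH and Free T4 draw (7.2.4) |
| 6 months (+2 weeks) | Mail | Unclear, as it is a contact and not a visit | Yes | None; FertiQoL to non-pregnant women (7.2.6) |
| Pregnancy follow-up, up to 15 months | Records | Not a visit | No | Record review includes AEs (7.2.5) |

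1. **Position of the mark.** The schedule has five columns: the four above plus screening. The FertiQoL row is marked at Time 0 and 6 months, and the pregnancy-record rows are marked in the last column. Against those rows, the single AE mark falls in the 6-month column. The count is 1 of 5 columns and 0 of 2 in-person visits.

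2. **Time 0.** Section 10.2 names the pain score as a safety parameter, and it is taken after infusion. A row that looks back to the test also has little to collect on the day of the test. What is missing is a prompt for immediate reactions other than pain.

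3. **2-4 weeks.** Nothing offsets the gap here. No AE mark and no AE wording appear, yet this is the last in-person study visit.

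4. **6 months.** The mark is present but the mailing has no AE content. Section 14.0 offers the gift card to "Participants who complete the FertiQol at final study contact", so the incentive does not attach to AE reporting either.

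5. **Timing.** Six months is 6 × 52/12 = 26 weeks. If only the schedule is followed, the first marked AE collection comes 26 − 4 = 22 to 26 − 2 = 24 weeks later than the 2-4 week inquiry that 10.4 implies. This is the delay in scheduled inquiry. It does not measure how long events stay unknown.

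6. **What remains in follow-up.** Record review (7.2.5, 6.2.2) covers all participants, including those who conceive. With the routes in 10.3, it will find events that reach a clinician. It does not ask the participant anything, so it is weakest for minor events not brought to care and for care received elsewhere.

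**The case against.** The strongest reply is that 10.4 already imposes the duty. Section 7.2.4 is headed as a visit, so an inquiry is due there, and the blank cell is only an incomplete table. On this reading the 6-month row is a cumulative final check alongside 10.4. That is a possible reading, but 7.2.4 and 7.2.6 omit AE questions in the same way as the table. The sections staff use to run the visits all point away from 10.4.

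Several further points stand and limit the finding.
- A reader might infer that the plan has no AE method in follow-up, or none for women who conceive. The documents do not support that: 7.2.5 and 6.2.2 name record review, and it covers everyone.
- A reader might infer that the team would learn of no AE, or hear nothing about pain, until six months. That is also unsupported. Procedural pain is scored the same day, 10.3 lets events surface at care, and 16.2 says women go straight into treatment in the same practice. Most non-pain parameters in 10.2 are serious sequelae, which records are more likely to show.
- A reader might infer bias between arms. None is shown. The trial is single-centre and double blind, so whichever section staff follow would apply to both arms.

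**Conclusion.** The inconsistency is real and should be corrected. It is clear at 2-4 weeks and softer at Time 0. At 6 months the mark stands but has no AE question behind it.

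The likely consequence is under-recording of early non-serious events, for an objective the protocol calls co-primary. This assumes that at least some staff work from the schedule and 7.2.4 in preference to 10.4, and that some minor events never reach the medical record. The documents give no AE rate or capture rate, so the number missed cannot be estimated. The count of women enrolled before the first marked inquiry would not be a substitute, since it says nothing about events missed. The pregnancy endpoint is unaffected.

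**What to change.** 1. In the 7.2 table, mark the AE row at 2-4 weeks, and at Time 0 after infusion for immediate reactions. Keep the 6-month mark, and reword the row label so that its look-back agrees with 10.4.
2. Add to 7.2.4: *In person or by phone around the time of the draw, study staff ask about pain, bleeding, infection, allergic reaction, symptoms of intravasation or embolism, and related surgery or hospitalisation since the procedure, and record the answers on the AE CRF.* These items come from 10.2 and section 11.0.
3. Add to 7.2.6: *A one-page AE form is sent to all participants, pregnant or not, asking about events since the last visit.* This look-back follows 10.4 and avoids reporting again what was recorded at 2-4 weeks.

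The cost is a few minutes of staff time per woman, one page in the 6-month mailing, and a mailing to women who conceived, for whom 7.2.6 currently describes none. The phone option allows for draws that study staff do not attend. Sample size, blinding and analysis do not change.

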10.5 Individuals reviewing the data

The safety review will be performed by the Steering Committee. The Steering Committee will be composed of the Study PI, [name], participating co-investigators in the Division of Reproductive Endocrinology, the Biostatistician, [name], and the study coordinator. The Steering Committee will meet in person regularly during the departmental research meeting to review progress and study issues.

